6.2 Data Adjustments, Handling, Conventions

All collected data will be presented in listings. Data not subject to analyses according to this plan will not appear in any tables or graphics but will be included only in the data listings.

Adverse events will be coded using the Medical Dictionary for Regulatory Activities (MedDRA) (version 16.1). Concomitant medications will be coded using World Health Organization Drug Dictionary (WHO-DD) (version March 1, 2013).

If partial dates occur, the convention for replacing missing dates for the purposes of calculating derived variables is as follows:

If an AE has a missing severity, it will be imputed as 'Severe'; any missing relationship to study drug of an AE will be imputed as 'Related'. No other missing data will be imputed unless otherwise specified.

In general, for quantitative laboratory values reported as '<' or ' \leq ', the lower limit of quantitation (LLOQ), or limit of detection (LOD), the reported value (i.e., LLOQ, LOD) will be used for analysis).

For quantitative laboratory values reported as '>' or ' \geq ', the upper limit of quantitation (ULOQ), the reported value (i.e., ULOQ) will be used for analysis.

For analysis purposes, repeat laboratory test results will not be used unless the original laboratory value is missing or indicated as invalid, in which case the first non-missing repeat laboratory value will be used for data analysis.

6.3 Derived and Computed Variables

The following derived and computed variables have been initially identified as important for the analyses of Safety, Efficacy and Exploratory endpoints. It is expected that additional variables may be required. The SAP will not be amended for additional variables that are not related to the primary target or key secondary target variables. Any additional derived or computed variables will be identified and documented in the SAS programs that create the analysis files. If the SAP is not amended, further derivations related to primary and secondary target variables will be described in the CSR.

- 302 Baseline = The last non-missing measurement/assessment on the date of Week 26 Visit from HZNP-ACT-301. If this measurement is missing or otherwise unavailable, it will be the last non-missing measurement/assessment on or prior to first dose in HZNP-

ACT-302.

- 301 Baseline = The last non-missing measurement/assessment prior to first dose of Study in HZNP-ACT-301.
- Study Day = Assessment Date – Date of Enrollment + 1
- Change from Baseline = Value at Post-Baseline – Value at Baseline
- Concomitant Medication is defined as any medication a subject has received concurrently with study treatment.
- Prior Medication is defined as any medication or therapies initiated prior to date of first dose of study drug. Medications that are started prior to the date of first dose of study drug and continue after the first dose of drug are considered to be both prior and concomitant medications.
- Treatment-Emergent Adverse Event (TEAE) – A TEAE is any adverse change from the subject's baseline condition that occurs on or after the date of the first dose of study drug through the duration of the clinical study.
- Related TEAE – Any TEAE with a reported relationship to study drug of 'possibly related'.
- Compliance = Calculated as the percentage of the number of vials used divided by the expected number of vials used, where the number of vials used is the number of used vials returned.

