9.4.2 Identity of Investigational Products

9.4.2.1 ACTIMMUNE

ACTIMMUNE (IFN- γ 1b) is a single-chain polypeptide containing 140 amino acids with a molecular weight of approximately 16,465 Daltons. IFN- γ 1b differs from natural human IFN- γ by the substitution of an additional N-terminal methionine, deletion/loss of seven amino acids and lack of glycosylation.

The commercial formulation of ACTIMMUNE is a sterile, clear, colorless solution filled in a single-use vial for SC injection. Each 0.5 mL of ACTIMMUNE contains: 100 μ g (2 million IU) of IFN- γ 1b formulated in 20 mg mannitol, 0.37 mg disodium succinate hexahydrate, 0.14 mg succinic acid, 0.05 mg polysorbate 20, and sterile water for injection.

The Sponsor will provide unlabeled, commercial ACTIMMUNE to CSM, Inc. The commercial formulation will be utilized, with each unlabeled vial containing ACTIMMUNE in a concentration of 200 μ g/mL. Each vial permits the extraction of up to 0.5 mL of ACTIMMUNE with additional volume to facilitate solution withdrawal. The study drug vials will be shipped to CSM, who will be responsible for labeling of the vials in accordance with regulatory guidelines (see [Section 9.4.3](#)). CSM will assemble kits containing three vials each, which will provide a sufficient quantity of study drug for one week of dosing until two vials per dose may be needed to deliver 100 μ g/m² depending on the BSA of the subject. When subjects reach the 100 μ g/m² TIW dose level, and two vials per dose are required, the same volume should be removed from

each vial and delivered in individual syringes. For example, if the dose should be 0.8 mL, then 0.4 mL should be withdrawn from each vial into separate syringes and two injections given.

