9.4.6 Drug Accountability

The Principal Investigator at each site is responsible for the control of all study medication. The site must maintain adequate records of the receipt and disposition of all study medication shipped to the study center. Records will include receipt dates, quantities received, quantities dispensed, quantities returned or destroyed, and the ID numbers of the subjects who received study medication.

All empty, partially empty, and full vials of study drug must be retained by the study center under locked storage, until drug accountability has been completed. Periodically throughout the study and at the conclusion of the study, inventory checks and accountability of study materials will be conducted by a representative of the Sponsor. Once accountability is completed, the Sponsor's representative will authorize the return of study medication (all used, partially used, and unused vials) to CSM. The completed Drug Accountability and Drug Return/Destruction Record(s) will be returned to the Sponsor. The investigator's copy of the Drug Accountability and Drug Return/Destruction Record(s) must document accurately the return of all study drug supplies. Records will also include disposition dates and quantities returned to the designated facility.

In addition, subjects or their caregivers can return biohazard containers supplied by study staff with all used syringes and needles from the study to study staff at the follow-up visit(s). Study staff will dispose of these containers appropriately.

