After Baseline/Day 1 (Week 26 of Study HZNP-ACT-301), subjects are scheduled to return to the clinic at Weeks 4, 13, and 26 during the treatment period. Study drug will be administered in the morning at the clinic at each of these visits. If the subject's next scheduled dose is the same day as the clinic visit, the dose will simply be given in the morning as opposed to bedtime for that particular day. If the subject is scheduled to dose the evening prior to the visit, the dose will be held and administered the next morning at the clinic. Bedtime dosing will be resumed after the clinic visit according to the subject's regular dosing schedule. For the TIW schedule, dosing should be Monday, Wednesday and Friday or alternatively Tuesday, Thursday and Saturday.

At Baseline/Day 1 (Week 26 of Study HZNP-ACT-301), subjects will be dispensed a 4-week supply of study drug for the dose-escalation period (up to 6 kits), and at Weeks 4 and 13, subjects and/or their caregivers will be dispensed a 6-week supply of study drug (up to 12 kits). Additional kits will be shipped to the subject's house between Weeks 4 and 13, and between Weeks 13 and 26, as needed. Subjects/caregivers may be dispensed the full supply at Weeks 4 and 13 if interim direct-to-subject shipments are not feasible. At Weeks 4, 13, and 26, subjects and/or their caregivers will return all unused kits and study drug vials.

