9.4.11 Treatment Compliance

Study medication will be dispensed at clinic visits, and re-supplies of study drug may be shipped in temperature-controlled containers to the subject's home. All unused study drug received by the subjects since the previous visit will be returned at the subsequent visit for drug accountability.

An inventory of the study medication supplies will be performed by the site or authorized study designee and recorded onto the Drug Accountability Log in the subject's source document records or equivalent.

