9.5.5.4 Week 26 (Termination Visit or Premature Withdrawal Visit)

- Collect all used, partially used, and unused study medication kits and vials.
- Collect blood (9.3 mL; 1.0 mL for hematology, 3.5 mL for chemistry, 3.0 mL discard, and 1.8 mL for PT/INR/aPTT) and urine samples from all subjects for safety clinical laboratory values (including urine pregnancy test [if applicable]).
- Collect blood samples (2 mL) for immunogenicity testing.
- Collect blood samples (1 mL) for frataxin analyses.
- Measure height and weight.
- Between approximately 7 to 10 AM, administer study drug or supervise administration of the study drug by either the subject or the subject's caregiver and record date/time of dosing.
- Perform physical examination, including vital signs.
- Enquire about AEs and concomitant medications.
- Perform ADL and Physician's and Patient's Global Assessments.
- Perform echocardiogram.
- Perform ECG.
- Perform Vision testing (LCSLC) and auditory testing (LiSN-S) if audiogram results were normal at Screening Visit of Study HZNP-ACT-301.
- Perform QOL assessments (PedsQL, SF-36, MFIS).
- Perform functional staging of FA and neurological assessments (FARS, T25FW, 9-HPT) at approximately 4 to 6 hours post-dose.
- Collect buccal samples and muscle biopsies (optional) for frataxin analysis.

Subjects will be released from the study center after all of the visit procedures have been completed and instructed to return in approximately two weeks for the Follow-Up Safety Visit.

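### The compliance numerator counts only used vials that come back, so a lost empty scores as a missed dose, and a vial count does not show the dose received

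*SAP*

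**What the plan says.** SAP 6.3 defines compliance as "the percentage of the number of vials used divided by the expected number of vials used" and adds that "the number of vials used is the number of used vials returned". SAP 9.6 summarises compliance and exposure over the whole study. It refers back to 6.3 for compliance and gives no derivation of exposure.

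The protocol describes returns in two ways.

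- **Unused drug named.** Section 9.4.11, the compliance section, says: "All unused study drug received by the subjects since the previous visit will be returned at the subsequent visit for drug accountability". Section 9.4.7.3 says that at Weeks 4, 13 and 26 "subjects and/or their caregivers will return all unused kits and study drug vials".
- **Used vials included.** The Week 4, 13 and 26 procedures (9.5.5.2 to 9.5.5.4) each say: "Collect all used, partially used, and unused study medication kits and vials". Section 9.4.6 says: "All empty, partially empty, and full vials of study drug must be retained by the study center under locked storage" until accountability is complete.

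On vial content, Protocol 9.4.2.1 says: "Each vial permits the extraction of up to 0.5 mL of ACTIMMUNE with additional volume to facilitate solution withdrawal". At 200 µg/mL that is 100 µg. The same section expects one vial per dose until the 100 µg/m² level, for which "two vials per dose may be needed to deliver" the dose, depending on body surface area (BSA).

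**The concern.** The numerator measures return behaviour as well as drug taken. Footnote 4 to the schedule of assessments places only the Week 4, 13 and 26 doses at the clinic, so almost every empty has to be kept at home and carried back. The two sections a site would most naturally consult on compliance and returns do not mention empties.

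The vial is also a coarse unit in a titration study. Doses are drawn by volume from single-use vials, so doses of quite different size can each consume one vial. Protocol 9.4.1.1 allows reductions and interruptions, so prescribed dose will differ between subjects.

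At stake is how the safety tables are read. Efficacy analysis has been dropped (SAP 2.2, 8 and 10), and compliance is the only drug-intake variable for which the SAP gives a formula. Protocol 9.2 describes the safety profile of the top dose level as unknown in children with this disease.

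**Working it through.** **Inputs.** Dose volume = level × BSA × 0.005 mL/µg, and BSA = √(in × lb / 3131) (Protocol 9.4.7.2). A vial holds 0.5 mL, or 100 µg, and kits hold three vials (9.4.2.1). The planned schedule is two doses at 10 µg/m² in the first week, then three doses a week at 25, 50 and 100 µg/m² from Days 8, 15 and 22 (9.4.1). Unused remainders are discarded (labeling in 17.2, item 2.2), so each dose opens at least one new vial.

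**The plan's own figures.** √(62 × 100 / 3131) = 1.407, rounded to 1.41 m². Then 25 × 1.41 × 0.005 = 0.176 mL, rounded to 0.18 mL. Both match 9.4.7.2. A six-week supply at two vials per dose is 6 × 3 × 2 / 3 = 12 kits, which matches the maximum in 9.4.7.3.

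**Non-return.** If a subject uses a fraction *a* of expected vials and returns a fraction *q* of the empties, SAP 6.3 gives compliance = *a* × *q*. The two factors cannot be separated. With *a* = 1 and assumed losses of 5%, 10% and 20%, the result is 95%, 90% and 80%. A subject with *a* = 0.9 and *q* = 1 also scores 90%.

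**Vials per dose.** This is the level × BSA / 100, rounded up. At 50 µg/m² one vial suffices when 50 × BSA ≤ 100, that is BSA ≤ 2.0 m². At 100 µg/m² one vial suffices only when BSA ≤ 1.0 m².

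**Course totals at BSA 1.41 m².** Doses: 2 + 3 + 3 + 69 = 77. Vials under the full plan: 8 × 1 + 69 × 2 = 146. Each row assumes that escalation stops at that level and every dose is taken.

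| Level reached (µg/m²) | mL per dose | Vials per dose | Course vials | Cumulative µg/m² | Share of planned dose |
|---|---|---|---|---|---|
| 10 | 0.07 | 1 | 77 | 77 × 10 = 770 | 10.8% |
| 25 | 0.176 | 1 | 77 | 20 + 75 × 25 = 1,895 | 26.5% |
| 50 | 0.35 | 1 | 77 | 20 + 75 + 72 × 50 = 3,695 | 51.7% |
| 100 | 0.705 | 2 | 146 | 20 + 75 + 150 + 6,900 = 7,145 | 100% |

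The first three rows score 77/146 = 52.7% if *expected* is the full plan, and 77/77 = 100% if it is the dose in force. Counting the Week 26 clinic dose separately gives 78 doses and 148 vials, and 78/148 is again 52.7%.

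**Used or partially used.** The visit procedures distinguish the two. At 1.41 m² every dosed vial keeps some drug: even at 100 µg/m², about 0.35 mL is drawn from each of two 0.5 mL vials. SAP 6.3 does not say whether such vials count as used.

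**The case against.** The strongest reply is that the protocol already requires empties back. Section 9.4.6 has the center hold them and later authorises their return to the supplier. Three sets of visit procedures collect them, and 9.5.5.1 collects used vials from the parent study, so subjects arrive familiar with the practice. Section 9.4.6 makes return of syringes and needles optional but gives no such latitude for vials. This stands. A reader might infer that the protocol asks for unused drug only, but neither 9.4.7.3 nor 9.4.11 says so, and the former can be read as unused kits plus vials. The fault is inconsistent wording beneath a fragile numerator.

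Other strong inferences also fail.

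- *Compliance could come out at 0%.* Some doses are given at the clinic, so some used vials are on site whatever subjects do at home.
- *Compliance in this study is biased downward by a known amount.* No return rate is given, and a vial opened but not fully injected would overstate intake.
- *A subject held at 50 µg/m² or below scores 53%.* That is one reading of an undefined denominator; the other gives 100%.
- *Vials never separate 10 from 50 µg/m².* Above 2.0 m² they do: 72 in and 175 lb gives 2.006 m², and 50 µg/m² then needs a second vial.
- *Dose by level will not be reported.* SAP 9.6 plans an exposure summary, SAP 6.3 lets further derivations be documented in programs, the planned table list is not legible in the copy available, and the eCRFs are not among the documents.

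Finally, dispensed minus unused returned has the opposite weakness: a full vial that is lost counts as taken. This also stands, and it is why one count should not simply replace the other.

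**Conclusion.** The point holds in a limited form. As written, SAP 6.3 cannot tell a lost empty from a missed dose, and the error from lost empties runs downward by exactly the non-return share. The 95% to 80% range rests on assumed losses of 5% to 20%. The protocol sections on returns do not agree and must be reconciled.

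The vial count does not stand in for dose. Up to 2.0 m², 10 and 50 µg/m² are indistinguishable, and at 1.41 m² a fully adherent subject held at or below 50 µg/m² scores 53% or 100% according to how *expected* is read. The missing definitions of *expected* and of exposure are gaps in detail; the main weakness is the numerator.

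The consequence is confined to description. There is one Safety Population (SAP 5), no inference is to be drawn (SAP 5.1), and no test, threshold or exclusion depends on compliance. The change is worth making because it is cheap and these summaries are the background to the adverse event tables.

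**What to change.** In SAP 6.3:

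1. Derive vials used as *D* − *U*, where *D* is vials dispensed (site plus direct shipment) and *U* is unused vials returned.
2. Report *R*, the returned used vials including partially used ones, beside it as a lower bound.
3. Show unaccounted-for vials, *D* − *U* − *R*, separately.
4. Compute expected vials from the prescribed dose level and BSA in force in each interval.

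In SAP 9.6, summarise cumulative prescribed dose under exposure. In the protocol, align 9.4.7.3 and 9.4.11 with 9.4.6 and the visit procedures on what is returned.

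An example shows the gain. Suppose 146 vials are dispensed and expected, and 131 used vials come back. If all were used and 15 empties lost, *D* − *U* = 146 with 15 unaccounted for. If 15 were not used and came back full, *D* − *U* = 131 with none unaccounted for. SAP 6.3 now scores both 131/146 = 90%.

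The cost is one revised definition, one added exposure summary and a wording alignment. Section 9.4.6 already requires quantities dispensed and returned. It is written around stock shipped to the study center, so the sponsor should confirm that direct-to-home shipments are logged in the same way. The downside is that an unreturned full vial counts as used in *D* − *U*; showing both counts keeps that visible.

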7. STUDY SUBJECTS AND DEMOGRAPHICS

7.1 Disposition of Subjects and Withdrawals

All subjects who provide informed consent/assent will be accounted for in this study. The number of subjects enrolled, completing, and withdrawing from the study, as well as reason for withdrawal, will be summarized by overall treatment. All disposition information will be included in a listing.

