This is a multi-center, dose-escalation, open-label extension study of HZNP-ACT-301 examining the safety and efficacy of ACTIMMUNE in the treatment of FA in children and young adults. Subjects who complete 26 weeks of blinded treatment in HZNP-ACT-301 will be eligible to enter this 6-month study. All subjects who choose to participate will receive ACTIMMUNE three times a week (TIW) for 26 weeks. In order to maintain the study blind in HZNP-ACT-301, all subjects in this open-label extension study will undergo ACTIMMUNE titration, regardless if they received ACTIMMUNE or placebo in HZNP-ACT-301. The study drug dose is planned to be escalated on a weekly basis over the first 4 weeks of treatment (from $10 \mu\text{g}/\text{m}^2$ to $100 \mu\text{g}/\text{m}^2$), however, the dose may be reduced, interrupted, or held based on tolerability. By Week 13, all subjects are to be on a stable tolerated dose of study drug in order to continue study participation; the dose may not be further increased after Week 13, however, it may be reduced on a case-by-case basis to manage subsequent drug-related adverse events (AEs) (e.g., elevated liver function tests).

The Week 26 Visit from HZNP-ACT-301 will serve as the Baseline Visit (Day 1) for this study. All subjects will undergo Baseline assessments and be assigned to the lowest dose ($10 \mu\text{g}/\text{m}^2$) of ACTIMMUNE. The first dose of study drug will be administered at home before bedtime according to the subject's TIW dosing schedule. During the treatment period, additional clinic visits are scheduled at Weeks 4, 13, and 26; in between clinic visits, subjects (and/or caregivers) will be monitored via emails/phone calls on a weekly basis until subjects reach their maximum tolerated dose and on a monthly basis thereafter.

Subjects will return to the clinic two weeks after the last dose of study drug for a Follow-Up Safety Visit.

An overview of the study design is presented in the schematic below, and details of study activities are provided in [Section 2.1, Schedule of Assessments](#).

Schematic of Study Design

¹ Week 26 of HZNP-ACT-301 will serve as the Baseline Visit (Day 1) for this study. Subjects will receive the last dose of the randomized drug from HZNP-ACT-301 in a double-blind fashion, and the first dose of study drug for the open-label extension study (10 $\mu\text{g}/\text{m}^2$) will be distributed for administration at home according to the planned TIW dosing schedule.

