8. STUDY OBJECTIVES

8.1 Primary Study Objective

The primary objective is to evaluate the long-term safety of ACTIMMUNE (IFN- γ 1b) in subjects with FA.

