9.3 Selection of Study Population

9.3.1 Inclusion Criteria

Eligible subjects must meet all of the following criteria:

1. Written informed consent and child assent, if applicable.
2. Completed 26 weeks of blinded treatment in Study HZNP-ACT-301.
3. If female, the subject is not pregnant or lactating or intending to become pregnant during the study, or within 30 days after the last dose of study drug. Female subjects of child-bearing potential must have a negative urine pregnancy test result at Baseline/Day 1 (Week 26 of Study HZNP-ACT-301) and agree to use a reliable method of contraception throughout the study and for 30 days after the last dose of study drug.

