9.3.2 Exclusion Criteria

Subjects will be ineligible if, in the opinion of the Investigator, they are unlikely to comply with the study protocol or have a concomitant disease or condition that could interfere with the conduct of the study or potentially put the subject at unacceptable risk.

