9.5.5.1 Baseline/Day 1 (Week 26 of Study HZNP-ACT-301)

The Week 26 Visit from HZNP-ACT-301 will serve as Baseline/Day 1 for this study. At the Baseline Visit, subjects will receive the last dose of the randomized drug from HZNP-ACT-301(ACTIMMUNE or placebo) in a double-blind fashion, and the first dose of study drug for the open-label extension study ($10 \mu\text{g}/\text{m}^2$) will be distributed for administration at home according to the planned TIW dosing schedule. Baseline assessments should be performed in the order presented below to ensure that the neurological tests are performed at approximately the same time on testing days.

- Collect all used, partially used, and unused study medication kits and vials from Study HZNP-ACT-301.
- Obtain signed, written Informed Consent/Assent and permission to use Protected Health Information (in accordance with the Health Insurance Portability and Accountability Act [HIPAA]) for Study HZNP-ACT-302. Refusal to provide this permission excludes an individual from eligibility for study participation. Record date Informed Consent/Assent was given and who conducted the process on the appropriate source documentation.
- Perform review of inclusion/exclusion criteria.
- Collect blood (9.3 mL; 1.0 mL for hematology, 3.5 mL for chemistry, 3.0 mL discard, and 1.8 mL for PT/INR/aPTT) and urine samples from all subjects for safety clinical laboratory values (including urine pregnancy test [if applicable]). The pregnancy test must be negative for those subjects to be eligible for participation in this study.
- Collect blood samples (2 mL) for immunogenicity testing.
- Collect blood samples (1 mL) for frataxin analyses.
- Measure height and weight to calculate dose volume.
- Educate subjects and caregivers on dosing technique and schedule.
- Between approximately 7 to 10 AM, administer the last dose of double-blind study drug for Study HZNP-ACT-301 or supervise administration of the study drug by either the subject or the subject's caregiver and record date/time of dosing.
- Perform physical examination, including vital signs.

- Enquire about AEs and concomitant medications.
- Perform ADL, and Physician's and Patient's Global Assessments.
- Perform echocardiogram.
- Perform ECG.
- Perform vision testing (LCSLC) and auditory testing (LiSN-S) if normal audiogram results at Screening Visit of Study HZNP-ACT-301.
- Perform QOL assessments (PedsQL, SF-36, MFIS).

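### Disposition starts at HZNP-ACT-302 consent and pools both HZNP-ACT-301 arms, so the planned withdrawal and TEAE rates mix selected HZNP-ACT-301 completers on drug with first-exposed subjects and give no 52-week denominator

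*SAP*

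**What the plan says.** **Entry.** Protocol 9.3.1 requires: "Completed 26 weeks of blinded treatment in Study HZNP-ACT-301". The Synopsis makes participation voluntary: "All subjects who choose to participate will receive ACTIMMUNE three times a week (TIW) for 26 weeks". Protocol 9.3.2 adds an investigator's judgement on compliance ("Subjects will be ineligible if, in the opinion of the Investigator, they are unlikely to comply with the study protocol") and on risk, excluding those who "have a concomitant disease or condition that could interfere with the conduct of the study or potentially put the subject at unacceptable risk".

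**Who is counted.** SAP 7.1 states: "All subjects who provide informed consent/assent will be accounted for in this study". The consent meant is the one for 302, taken at the 301 Week 26 visit (Protocol 9.5.5.1: "Obtain signed, written Informed Consent/Assent and permission to use Protected Health Information"). SAP 7.1 then summarises "The number of subjects enrolled, completing, and withdrawing from the study", with reasons for withdrawal, by overall treatment. The Safety Population in SAP section 5 also requires at least one open-label dose.

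**How results are split.** SAP sections 6, 7.1 and 9.1 present summaries by overall treatment, a term the SAP does not define. The protocol's Synopsis (Statistical Analyses) promises every summary both by treatment received in 301 and overall. SAP section 10 declares only the removal of the efficacy analyses.

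**Purpose.** Protocol 8.1: "The primary objective is to evaluate the long-term safety of ACTIMMUNE". SAP 2.2 and section 8 say the output is an abbreviated safety report.

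**The concern.** A subject randomised to ACTIMMUNE in 301 reaches 302 only after 26 weeks of treatment on drug, a decision to go on and an investigator's agreement. Those who stopped in 301, for intolerance or any other reason, and those who declined to continue are outside every 302 denominator. A former-placebo subject passes the same formal criteria but has not been filtered by exposure to the drug. The two streams are selected differently, and the SAP adds them together.

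This matters because the only subjects with up to 52 weeks of exposure are the former-ACTIMMUNE ones, and long-term safety is the primary objective. Protocol 7.3 says that titration is meant to limit initial poor tolerability and dropout, so the sponsor expects losses to concentrate early. For the former-ACTIMMUNE stream, first exposure lies in 301. Protocol 9.5.3.1.2 also treats adverse events ongoing from 301 as baseline signs or symptoms. Protocol 9.2 describes 301 completers as consistent with the target population, and the readable SAP text adds no caveat. A reader who has only the 302 tables could not tell how many ACTIMMUNE starters were lost before those tables begin, or why.

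**Working it through.** The documents give no 301 attrition, roll-over proportion, allocation ratio or planned 302 withdrawal rate, so there is no stated figure to reproduce. Every rate below is an assumption. Two separate questions need two calculations.

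**1. How far could the pooled 302 rate differ from the first-exposure rate over the same 26 weeks?**

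Assumptions: 1:1 allocation in 301; a share s of subjects is intolerant and withdraws with probability p per 26 weeks on drug; the others withdraw at 3%; 97% of placebo subjects complete 301; every completer rolls over.

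- First-exposure withdrawal: r1 = s·p + (1 − s)·0.03
- Intolerant share among completers on drug: s2 = s(1 − p)/(1 − r1)
- Withdrawal in 302 among former-ACTIMMUNE subjects: r2 = s2·p + (1 − s2)·0.03
- Pooled 302 rate: [(1 − r1)·r2 + 0.97·r1] / [(1 − r1) + 0.97]

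For s = 0.20 and p = 0.50:

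- r1 = 0.100 + 0.024 = 0.124
- s2 = 0.100/0.876 = 0.114
- r2 = 0.057 + 0.027 = 0.084
- pooled = (0.876 × 0.0837 + 0.97 × 0.124)/1.846 = 0.105

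First exposure over pooled is 0.124/0.105 = 1.18. First exposure over continuing is 0.124/0.084 = 1.48.

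| s | p | First exposure | Continuing | Pooled 302 | First ÷ pooled |
|---|---|---|---|---|---|
| 0.10 | 0.30 | 5.7% | 5.0% | 5.4% | 1.06 |
| 0.20 | 0.50 | 12.4% | 8.4% | 10.5% | 1.18 |
| 0.20 | 0.70 | 16.4% | 7.8% | 12.4% | 1.32 |
| 0.30 | 0.70 | 23.1% | 10.8% | 17.7% | 1.31 |

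Over s = 0.10 to 0.30 and p = 0.30 to 0.70, the continuing rate is always below the first-exposure rate, the pooled rate lies between them, and first exposure is about 1.06 to 1.3 times pooled. The model assumes fixed intolerance, so it bears on tolerability withdrawal only. It says nothing about toxicity that builds up late, and TEAE rates are not quantified.

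**2. What 52-week figure would a 302-only table leave out?**

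Let a be the proportion of 301 ACTIMMUNE subjects who stop before Week 26, and let 5% withdraw in 302, with all completers rolling over. Cumulative withdrawal = 1 − (1 − a)(1 − 0.05):

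- a = 5%: 1 − 0.95 × 0.95 = 9.8%
- a = 10%: 1 − 0.90 × 0.95 = 14.5%
- a = 20%: 1 − 0.80 × 0.95 = 24.0%

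The 302 table would show 5% for this stream in each case. If a further 10% of completers do not roll over, the proportion without complete 52-week data is 1 − (1 − a)(0.90)(0.95), which is 18.8%, 23.1% and 31.6%.

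These are cumulative figures over twice the time. In the first case the withdrawal rate is 5% in both periods, so there is no selection effect at all, yet the 52-week figure is still 9.8%. The calculation shows what is missing from the report, not how biased it is.

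**The case against.** The case against has several sound parts.

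- **Starting an extension's disposition at its own consent is usual.** 301 is a separate trial, and its attrition by arm may be in its own report, which is not available here. The completer restriction is also stated openly in SAP sections 3 and 5.1. This stands, and it makes the point an improvement rather than an error. It does not supply a link between the two studies for subjects whose exposure spans both.
- **A reader might infer that the 302 rates describe tolerant survivors.** The documents do not support that. The planned columns pool in first-exposed former-placebo subjects, completing 26 weeks does not prove tolerance because how 301 handled dose reduction is not described, and all subjects are re-titrated in 302.
- **A reader might set 9.8% to 24.0% against 5% and infer a two- to five-fold understatement.** That compares 52 weeks with 26 and is not a measure of bias.
- **A reader might infer that the sponsor will present the 302 rates as applying to anyone starting the drug.** That would be drawn from the stated objective and the missing caveat. No SAP text says it, and SAP 5.1 says that no inference will be drawn from any statistical tests.
- **Absence is not fully proven.** The planned-tables list in SAP section 13 cannot be read in the public copy, and SAP 9.2 refers to shift tables by treatment group, so a split by 301 arm is possible though undefined.

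What remains is that no readable text gives 301 attrition, a 52-week denominator, or a statement of whom the former-ACTIMMUNE rates describe.

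**Conclusion.** The point holds in a limited form. As SAP 7.1 reads, withdrawal and TEAE rates combine a stream selected by completing 301 on ACTIMMUNE and agreeing to continue with a stream first exposed in 302. In the first stream the rates are conditional on 301 completion. Understatement of early tolerability withdrawal among all starters is the probable direction; for late or cumulative toxicity the direction is not established.

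The size cannot be determined from these documents and could be near zero. The illustrated like-for-like effect on the pooled withdrawal rate is modest and rests on the two-class model, 1:1 allocation and full roll-over. The firmer consequence is that a report whose primary objective is long-term safety would, on the readable plan, carry no 52-week discontinuation figure with all ACTIMMUNE starters as denominator. The undeclared loss of the protocol's split by 301 treatment makes this harder to see. The change is worth making because it is cheap, not because a large bias has been shown.

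**What to change.** 1. In SAP 7.1, present disposition by 301 treatment and overall, as the protocol's Synopsis promises. Start from 301: randomised; discontinued, by reason; completed; not rolled over (declined or not eligible); enrolled in 302; dosed; completed 302.
2. For the 301 ACTIMMUNE arm, add cumulative discontinuation, overall and for adverse events, from first 301 dose to Week 52, with all 301-treated subjects as denominator. Show subjects who completed 301 but did not roll over on their own line, so that they are not read as withdrawals for intolerance.
3. State in SAP section 9 that 302 rates in former-ACTIMMUNE subjects apply to 301 completers who chose to continue.

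The cost is one extended table, produced after 301 unblinding, and one sentence. No new data are collected, and the SAP already draws on 301 for demographics and baseline values (sections 6.3 and 7.3). The drawback for the sponsor is a less favourable discontinuation figure.
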